17.1. Appendix 1: Time and Event Schedule

Assessment	V1: Screening/ Enrollment (30 days) ¹⁵	V2: Cordella PA Sensor Implant Visit	V3: Month 1 (±7 days)	V4 ¹¹ : Month 3 (±7 days)	V5: Month 6 (±14 days)	V6: Month 12 (±30 days)	V7 to V8: Months 18, 24 (±30 days)	V9 to V11 Year 3, 4, 5 (±30 days)
Informed Consent	X							
Subject Demographics	X							
Study Eligibility Review and Committee Approval	X							
Cardiac/Medical & Surgical History	X							
Physical Exam, height, weight, and vital signs ^{1,5}	X	X	X ¹²		X	X	X	X
12-Lead ECG with Interpretation	X				X	X	X ⁴	X
Urinalysis ²	X							
Safety Labs (Chemistry/Hematology/ aPTT/ INR)	X				X	X	X ⁴	X
Serum NT-pro BNP	X		X	X ¹²	X	X	X	X
aPTT/ INR (if indicated)								
Echocardiogram ³	X					X		X
Subject Training: Cordella™ HF System ¹⁴	X							
Subject Training: CorPASS		X						
Cordella™ PA Sensor Implant		X						
Cordella System Use (daily)	X	X	X	X	X	X	X	X
Cordella™ PAP – dia/sys/mean/pulse		X ⁹	X ^{5,6}	X ^{5,6}	X ^{5,6}	X ^{5,6}	X ^{5,6}	X ⁶
RHC PAP / RAP/ PCWP/ CO/ CI/ RVP ⁸		X						X ¹²
Subject Status	X		X	X	X ¹⁰	X ¹⁰	X	X
6- Minute Walk Test	X				X	X ⁷	X ^{4,7}	X ⁷
NYHA Functional Classification	X ¹⁶		X	X	X	X	X	X
KCCQ Quality of Life Questionnaires ⁵	X		X	X	X	X	X	X
Concurrent/Cardiac Medications	X	X	X	X	X	X	X	X
Adverse Events	X	X	X	X	X	X	X	X
Health Economic Questionnaire							X ⁴	
Subject Survey (optional)/ Cohort #1 only ¹³	1. Month 1 after Unblinding 2. Quarterly until V11 / Year 5							
Site Survey (optional)/ Cohort #1 only ¹³	1. Month 1 after Unblinding 2. Quarterly until V11 / Year 5							
1. Full Physical Examination and Height performed at Screening Visit only 2. Urine (V1) pregnancy test for females				8. Additional RHC as needed for Re-calibration purposes at the clinician’s discretion 9. Via CalEQ				

This document is confidential.


3. Echo may be obtained within 3 or 6 months of Screening details are in protocol section 8.1.10 4. At Month 24 only 5. via myCordella™ Patient App at home prior to visit. Baseline KCCQ will be completed on myCordella tablet following Cordella System distribution at Screening Visit 6. via myCordella™ Patient App sitting and supine 7. Additional PAP Measurements will be obtained before and after 6-minute walk test
	
10. Incl. question on assigned treatment at Visit 5 and 6 11. Visit should be completed remote/virtually 12. If available 13. After subject gets unblinded to PAP Pressures at V6 or cross-over whatever comes first 14. Subject training on and distribution of the commercial Cordella™ System (should occur at Screening Visit (Visit 1). 15. Some study procedures need to be repeated in case a subject is implanted >30 days after Visit 1, details are in protocol section 8.3.1 16. may be obtained within the 30 day Study Visit 1 window 17. At V9 / Year 3 only

---	---

17.2. Appendix 2: The Kansas City Cardiomyopathy Questionnaire Scoring Instructions

Note: references to “**means of questions actually answered**” imply the following.

If there are n questions in a scale, and the subject must answer m to score the scale, but the subject answers only $n-i$, where $n-i \geq m$, calculate the **mean of those questions** as (sum of the responses to those $n-i$ questions) / $(n-i)$
not
 (sum of the responses to those $n-i$ questions) / n

There are 10 summary scores within the KCCQ, which are calculated as follows:

1. Physical Limitation

Code responses to each of Questions 1a-f as follows:

Extremely limited = 1

Quite a bit limited = 2

Moderately limited = 3

Slightly limited = 4

Not at all limited = 5

Limited for other reasons or did not do = <missing value>

If at least three of Questions 1a-f are not missing, then compute

Physical Limitation Score = $100 * [(mean\ of\ Questions\ 1a-f\ actually\ answered) - 1] / 4$

2. Symptom Stability

•Code the response to Question 2 as follows:

This document is confidential.

Much worse = 1

Slightly worse = 2

Not changed = 3

Slightly better = 4

Much better = 5

I've had no symptoms over the last 2 weeks = 3

If Question 2 is not missing, then compute

Symptom Stability Score = $100 * [(Question\ 2) - 1] / 4$

3. Symptom Frequency

Code responses to Questions 3, 5, 7 and 9 as follows:

Question 3

Every morning = 1

3 or more times a week but not every day = 2

1-2 times a week = 3

Less than once a week = 4

Never over the past 2 weeks = 5

Questions 5 and 7

All of the time = 1

Several times a day = 2

At least once a day = 3

3 or more times a week but not every day = 4

1-2 times a week = 5

Less than once a week = 6

Never over the past 2 weeks = 7

Question 9

Every night = 1

This document is confidential.

3 or more times a week but not every day = 2

1-2 times a week = 3

Less than once a week = 4

Never over the past 2 weeks = 5

If at least two of Questions 3, 5, 7 and 9 are not missing, then compute:

$$S3 = [(Question\ 3) - 1]/4$$

$$S5 = [(Question\ 5) - 1]/6$$

$$S7 = [(Question\ 7) - 1]/6$$

$$S9 = [(Question\ 9) - 1]/4$$

$$\text{Symptom Frequency Score} = 100 * (\text{mean of } S3, S5, S7 \text{ and } S9)$$

4. Symptom Burden

Code responses to each of Questions 4, 6 and 8 as follows:

Extremely bothersome = 1

Quite a bit bothersome = 2

Moderately bothersome = 3

Slightly bothersome = 4

Not at all bothersome = 5

I've had no swelling/fatigue/shortness of breath = 5

If at least one of Questions 4, 6 and 8 is not missing, then compute

$$\text{Symptom Burden Score} = 100 * [(\text{mean of Questions 4, 6 and 8 actually answered}) - 1]/4$$

5. Total Symptom Score

= mean of the following available summary scores: Symptom Frequency Score and Symptom Burden Score

6. Self-Efficacy

Code responses to Questions 10 and 11 as follows:

Question 10

Not at all sure = 1

Not very sure = 2

Somewhat sure = 3

This document is confidential.

Mostly sure = 4

Completely sure = 5

Question 11

Do not understand at all = 1

Do not understand very well = 2

Somewhat understand = 3

Mostly understand = 4

Completely understand = 5

If at least one of Questions 10 and 11 is not missing, then compute

Self-Efficacy Score = $100 * [(\text{mean of Questions 10 and 11 actually answered}) - 1] / 4$

7. Quality of Life

Code responses to Questions 12, 13 and 14 as follows:

Question 12

It has extremely limited my enjoyment of life = 1

It has limited my enjoyment of life quite a bit = 2

It has moderately limited my enjoyment of life = 3

It has slightly limited my enjoyment of life = 4

It has not limited my enjoyment of life at all = 5

Question 13

Not at all satisfied = 1

Mostly dissatisfied = 2

Somewhat satisfied = 3

Mostly satisfied = 4

Completely satisfied = 5

Question 14

I felt that way all of the time = 1

This document is confidential.

I felt that way most of the time = 2

I occasionally felt that way = 3

I rarely felt that way = 4

I never felt that way = 5

If at least one of Questions 12, 13 and 14 is not missing, then compute

Quality of Life Score = $100 * [(\text{mean of Questions 12, 13 and 14 actually answered}) - 1] / 4$

8. Social Limitation

Code responses to each of Questions 15a-d as follows:

Severely limited = 1

Limited quite a bit = 2

Moderately limited = 3

Slightly limited = 4

Did not limit at all = 5

Does not apply or did not do for other reasons = <missing value>

If at least two of Questions 15a-d are not missing, then compute

Social Limitation Score = $100 * [(\text{mean of Questions 15a-d actually answered}) - 1] / 4$

9. Overall Summary Score

= mean of the following available summary scores: Physical Limitation Score, Total Symptom Score, Quality of Life Score, Social Limitation Score

10. Clinical Summary Score

= mean of the following available summary scores: Physical Limitation Score, Total Symptom Score

This document is confidential.

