***Excerpted from the American Thoracic Society, ATS Statement: Guidelines for the Six-Minute Walk Test, March 2002.**

14.4 Kansas City Cardiomyopathy Questionnaire

THE KANSAS CITY CARDIOMYOPATHY QUESTIONNAIRE:

The following questions refer to your **heart failure** and how it may affect your life. Please read and complete the following questions. There are no right or wrong answers. Please mark the answer that best applies to you.

1. **Heart failure** affects different people in different ways. Some feel shortness of breath while others feel fatigue. Please indicate how much you are limited by **heart failure** (shortness of breath or fatigue) in your ability to do the following activities over the past 2 weeks.

Place an X in one box on each line

Activity	Extremely Limited	Quite a bit Limited	Moderately Limited	Slightly Limited	Not at all Limited	Limited for other reasons or did not do the activity
Dressing yourself						
Showering/Bathing						
Walking 1 block on level ground						
Doing yardwork, housework or carrying groceries						
Climbing a flight of stairs without stopping						
Hurrying or jogging (as if to catch a bus)						

2. Compared with 2 weeks ago, have your symptoms of **heart failure** (shortness of breath, fatigue or ankle swelling) changed? My symptoms of **heart failure** have become . . .

Much worse	Slightly worse	Not changed	Slightly better	Much better	I've had no symptoms over the last 2 weeks
					

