5.2. Key Definitions

Age

Age at screening is derived in the database and this value will be used for all analyses.

Definition of Baseline for safety assessments

Baseline will be defined as the last available value prior to the implant of Cordella PA Sensor and may be at any visit between Screening (V1) and Cordella PA Sensor Implant Visit (V2).

Definition of Baseline for PAP measurements

Baseline will be defined as value at Implant Visit (V2) obtained before discharge .

Change from Baseline

Absolute change from baseline:

Absolute change = Post-baseline value –baseline value

Time to Onset of AE

Time to onset of AE [days] = Date of start of AE – Date of implant of Cordella PA Sensor + 1

Start Day of concomitant medication

If medication starts before date of implant of Cordella PA Sensor:

Start Day of Medication = Date of start of medication – Date of implant of Cordella PA Sensor

If medication starts at/after date of implant of Cordella PA Sensor

Start Day of Medication = Date of start of medication – Date of implant of Cordella PA Sensor + 1

Incomplete start dates of medication will not be imputed. Start day of medication will be missing.

Stop Day of concomitant medication

If medication stopped before date of implant of Cordella PA Sensor:

Stop Day of Medication = Date of end of medication – Date of implant of Cordella PA Sensor

If medication stops at/after date of implant of Cordella PA Sensor

This document is confidential.

Stop Day of Medication = Date of end of medication – Date of implant of Cordella PA Sensor + 1
Incomplete end dates of medication will not be imputed. Stop day of medication will be missing.

Definition of study completed/discontinued/ongoing

A subject will be defined as study ‘completed’/‘discontinued’ based on the eCRF information. At the time of the pre-defined main analysis, subjects which are ongoing at date of cut-off will be counted as ‘ongoing’.

Time since first diagnosis of heart failure

Time since diagnosis [months] = ((Date of Screening – Date of first HF diagnosis)+1)/30

Exposure time:

which would be exact 6 or 12 months (180 or 365 days respective) post-implant visit for subjects who are still in the study at/after this timepoint.

which would be [date of last available date – date of Implant visit + 1] for subjects who withdraw from study prior to month 6 or 12 (180 or 365 days respective) post-implant visit.

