7.1.16. Subject Outcome Measures, measured by Quality of Life KCCQ questionnaire

The Quality of Life KCCQ questionnaire is a measure of health-related quality of life. Data will be collected at the study visits described in [Appendix 1: Time and Event Schedule](#). For the analysis of this endpoint, external data, provided by Endotronix, will be used.

The KCCQ is a 23-item, refer to Protocol, section 14.4, self-administered instrument that quantifies physical function, symptoms (frequency, severity, and recent change), social function, self-efficacy and knowledge, and quality of life related to HF.

Out of 23-items, 10 scores will be calculated according to the rules in [Appendix 2: The Kansas City Cardiomyopathy Questionnaire Scoring Instructions](#): Physical Limitation, Symptom Stability, Symptom Frequency, Symptom Burden, Total Symptom Score, Self-Efficacy, Quality of Life, Social Limitation, Overall Summary Score, Clinical Summary Score.

Presentation will be done by means of descriptive statistics including the absolute value and change from baseline by visit.

Analysis will be done based on mITT population, PP population, and Cohort #1 population. Prior to the date of cut-off for the main analysis, it will be confirmed, if analysis based on PP population will be required.

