	14.2.2.11.8	Comparison between Cordella Sensor PA measurement before and after 6-Minute walk test by visit	Per Protocol Population
14.2.2.12		Percentage of device success as documented by ability of the System to successfully transmit collected PAP data	
	14.2.2.12.1	Device success rate to transmit collected PAP data	mITT Population
	14.2.2.12.2	Device success rate to transmit collected PAP data	Per Protocol Population
	14.2.2.12.3	Device success rate to transmit collected PAP data	Cohort #1 Population
14.2.2.13		Quality of Life KCCQ questionnaire	
	14.2.2.13.1	Kansas City Cardiomyopathy Questionnaire (KCCQ): Summary for overall and domain scores by visit and change from baseline	mITT Population
	14.2.2.13.2	Kansas City Cardiomyopathy Questionnaire (KCCQ): Summary for overall and domain scores by visit and change from baseline	mITT Population
	14.2.2.13.3	Kansas City Cardiomyopathy Questionnaire (KCCQ): Summary for overall and domain scores by visit and change from baseline	mITT Population
	14.2.2.13.4	Kansas City Cardiomyopathy Questionnaire (KCCQ): Summary for overall and domain scores by visit and change from baseline	Per Protocol Population
	14.2.2.13.5	Kansas City Cardiomyopathy Questionnaire (KCCQ): Summary for overall and domain scores by visit and change from baseline	Cohort #1 Population
14.2.2.14		Functional status improvement	
	14.2.2.14.1	Shifts in NYHA functional classification from baseline to post-baseline visits	mITT Population
	14.2.2.14.2	Shifts in NYHA functional classification from baseline to post-baseline visits, stratified by sex	mITT Population
	14.2.2.14.3	Shifts in NYHA functional classification from baseline to post-baseline visits, stratified by heart failure ejection fraction	mITT Population
	14.2.2.14.4	Shifts in NYHA functional classification from baseline to post-baseline visits	Per Protocol Population

This document is confidential.

Header	Table Number	Name	Analysis Set
	14.2.2.14.5	Shifts in NYHA functional classification from baseline to post-baseline visits	Cohort #1 Population
	14.2.2.14.6	Six (6)-Minute walk, summary by visit and change from baseline	mITT Population
	14.2.2.14.7	Six (6)-Minute walk, summary by visit and change from baseline, stratified by sex	mITT Population
	14.2.2.14.8	Six (6)-Minute walk, summary by visit and change from baseline, stratified by heart failure ejection fraction	mITT Population
	14.2.2.14.9	Six (6)-Minute walk, summary by visit and change from baseline	Per Protocol Population

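### Change from baseline is planned for the KCCQ Symptom Stability score, which is already a two-week change item, so the tabulated difference is not a change since implant

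*SAP*

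**What the plan says.** SAP 7.1.16 derives ten scores from the KCCQ, and the list includes Symptom Stability: "Physical Limitation, Symptom Stability, Symptom Frequency, Symptom Burden, Total Symptom Score", and so on. It then sets one rule for all ten: "Presentation will be done by means of descriptive statistics including the absolute value and change from baseline by visit". No score is excepted. The SAP's index of tables (section 14) carries the same plan into Tables 14.2.2.13.1 to 14.2.2.13.5, titled "Summary for overall and domain scores by visit and change from baseline". SAP 5.2 defines the change as "Absolute change = Post-baseline value –baseline value". The schedule in SAP Appendix 1 places the baseline KCCQ at the Screening Visit.

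The Symptom Stability score rests on Question 2 alone. In Protocol 14.4 that question begins "Compared with 2 weeks ago, have your symptoms of" and offers five answers from much worse to much better, plus a sixth for subjects who had no symptoms. SAP Appendix 2 codes the five answers 1 to 5 and the sixth as "no symptoms over the last 2 weeks = 3", the same code as an unchanged subject.

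**The concern.** A change from baseline is informative when the score describes the subject's state at each visit. Nine of the ten KCCQ scores do this or are built from scores that do. Symptom Stability does not: each answer is itself a change, over the two weeks before the questionnaire. The screening answer covers the two weeks before screening, and the Month 6 answer covers the two weeks before Month 6, about 14 of the 180 days since implant. Their difference says whether the recent trend differs between the two occasions. It does not say whether the subject is better or worse than at implant, although the table title will present it that way.

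The protocol's own picture of treatment makes this more than a corner case. Protocol 8.1.20 expects one to three months of intensive optimization and then a stable phase. A subject who improves early and keeps the gain would properly answer that nothing changed in the last two weeks before Month 6. If that subject was also stable at screening, the tabulated change is 0.

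KCCQ is secondary efficacy endpoint 13 in a single-arm trial, so the main tables have no concurrent comparator that would show a difference of this kind to be an artefact. At stake is one row of descriptive output that cannot be read as labelled.

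**Working it through.** **Inputs.** Codes for Question 2: much worse 1, slightly worse 2, not changed 3, slightly better 4, much better 5, no symptoms 3 (SAP Appendix 2). Score = 100 × (code − 1) / 4 (SAP Appendix 2). Change = post-baseline score − baseline score (SAP 5.2). The plan states no figure of its own here to reproduce.

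**Step 1: scores.** Much worse 0; slightly worse 25; not changed 50; slightly better 75; much better 100; no symptoms 50.

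**Step 2: change for individual subjects.**

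| Screening answer | Follow-up answer | Score change | What happened to the subject |
|---|---|---|---|
| Not changed (50) | No symptoms (50) | 0 | Symptoms resolved |
| Slightly worse (25) | Not changed (50) | +25 | Stayed at the worse level (if nothing changed in between) |
| Much worse (0) | Not changed (50) | +50 | Stayed at the worse level (if nothing changed in between) |
| Slightly better (75) | No symptoms (50) | −25 | Symptoms resolved |
| Much better (100) | No symptoms (50) | −50 | Symptoms resolved |

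The difference can be positive with no improvement since screening, and zero or negative with complete relief of symptoms.

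**Step 3: mean change in a group.** The documents do not give the screening distribution of Question 2, so it has to be assumed. Suppose every subject answers not changed at follow-up, so that the follow-up mean is 50. The mixes are given as slightly worse / not changed / slightly better.

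- 20/70/10%: baseline mean = 0.20×25 + 0.70×50 + 0.10×75 = 5 + 35 + 7.5 = 47.5; change = 50 − 47.5 = +2.5.
- 10/70/20%: baseline mean = 0.10×25 + 0.70×50 + 0.20×75 = 2.5 + 35 + 15 = 52.5; change = 50 − 52.5 = −2.5.
- Any mix with equal shares slightly worse and slightly better: baseline mean 50; change 0.

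The sign follows from the assumed mix alone.

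**Step 4: reach.** Appendix 2 builds the Total Symptom Score from Symptom Frequency and Symptom Burden only. The Overall Summary Score is the "mean of the following available summary scores: Physical Limitation Score, Total Symptom Score, Quality of Life Score, Social Limitation Score", and the Clinical Summary Score uses the first two of these. Symptom Stability enters none of the three. A symptom-free subject scores 100 on Symptom Frequency (each of S3, S5, S7 and S9 equals 1) and 100 on Symptom Burden (100 × (5 − 1)/4), so relief of symptoms is recorded elsewhere in the same tables.

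**The case against.** The strongest reply is that little depends on this. The KCCQ analysis is descriptive, with no hypothesis test. SAP 2.4.2 treats p-values for secondary endpoints beyond the first as nominal. Nine other scores are reported, and those that measure symptoms directly show full improvement in a symptom-free subject. The visit value of Symptom Stability is already planned, so a careful reader could disregard the change column. All of this stands, and it limits the weight of the point. It does not make the subtraction meaningful.

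A reader might also infer that coding no symptoms as 3 is an error. The documents do not support that. On a stability item, a subject with no symptoms is a stable subject, and the midpoint is coherent. The fault lies in the presentation rule of SAP 7.1.16, not in Appendix 2.

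A reader might infer that the artefact flatters the device, because subjects may enter after a deterioration. The documents do not support a direction. Protocol 7.1 describes subjects as clinically stable, inclusion criterion 4 asks for at least 30 days of stable therapy, and nothing is said about screening answers to Question 2.

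Finally, a reader might extend the criticism to the Overall and Clinical Summary Scores, since they average whichever domains are available and a change could compare different domains. That is the scoring rule that Appendix 2 sets out. An individual subject can be constructed for whom it matters, but the documents give no frequency, and the domain scores are tabulated alongside. A same-domain comparison would be a preference, not a correction.

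**Conclusion.** Wrong as written, minor. The SAP applies change from baseline to a score that already measures change, and labels the result as if it described the subject since baseline. For individual subjects the result can be +25 or +50 with no improvement since screening, and 0, −25 or −50 with complete relief of symptoms. These values follow directly from the SAP's coding and its definition of change; the positive cases assume that the subject simply stayed at the screening level.

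The size and direction of a mean effect cannot be derived from the documents. The values of +2.5 and −2.5 are illustrations under assumed screening mixes with every subject unchanged at follow-up. The effect is limited to one of ten descriptive scores. The Total Symptom, Overall Summary and Clinical Summary scores, the primary endpoints, the gated 12-month endpoint, type I error and power are all unaffected.

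**What to change.** In SAP 7.1.16, restrict change from baseline to the nine scores other than Symptom Stability. For Symptom Stability, report by visit only: the score as already planned, plus the number and percentage of subjects giving each of the six Question 2 answers, so that unchanged and symptom-free subjects can be told apart. Edit the shells of Tables 14.2.2.13.1 to 14.2.2.13.5 to match. Leave the Appendix 2 coding and all visit scores as they are. The cost is one SAP sentence and a table-shell edit, with no new data and no effect on any test.
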